Study Protocol and Statistical Analysis Plan

Title of Study: The Effect of Graded Motor Imagery on Pain and Function in Individuals with Knee Osteoarthritis: a Comparative Randomized Controlled Trial NCT Number: NCT05925517 Date of Document: March 31, 2024

Table of contents

	Table of contents	
		Page number
Study Protocol		3
Objectives		3
Design		3
Methods		3
Statistical Analysis Plan		4

Study Protocol

Objectives:

The objective of this study was to investigate whether Graded Motor Imagery (GMI) shows comparable effectiveness to Transcutaneous Electrical Nerve Stimulation (TENS) in improving pain and functionality in individuals diagnosed with knee osteoarthritis (PwKOA).

Design:

A small randomized controlled trial design was conducted online at three time points: 1) baseline/pre-test, 2) post-test (after the 8-week intervention), and 3) follow-up (6-week follow-up). Data were collected by face-to-face interview method.

Participants will be randomly assigned to one of two conditions: 1) GMI or 2) TENS. One group underwent GMI treatment, while the other group received TENS therapy three times a week for 8 weeks. Additionally, both groups engaged in home-based and functional exercises.

The study was approved by the Marmara University Faculty of Medicine Clinical Research Ethics Committee (date: 02/06/2023, procedure number: 09.2023.795) and was by the ethical standards of the World Medical Association (Declaration of Helsinki).

Methods:

Sample and Recruitment. Patients diagnosed with unilateral knee osteoarthritis (KOA) were included in the study. To participate in the research, the following criteria must be met: 1) Grade II-III KOA as per the Kellgren and Lawrence classification and American College of Rheumatology (ACR) criteria, accompanied by symptoms and radiographic evidence; 2) experience moderate to severe pain rated as three or higher on the Visual Analog Scale (VAS) during activity; 3) participants must score at least 24 points on the Mini-Mental State Examination (MMSE); 4) age of the participants should be between 45 and 64 years. Patients diagnosed by an orthopedist were treated by a certified physiotherapist at Artvin State Hospital between 1 July 2023 and 31 March 2024.

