Procedure. Throughout the GMI protocol, participants engaged in three weeks of lateralization, followed by three weeks of motor imagery (MI), and concluded with two weeks of mirror therapy (MT). Lateralisation training was conducted using the RecogniseTM Knee app. The four-stage program included 20 different knee images in each stage, with a viewing time of 5 seconds, progressing from easy to difficult (Basic, Vanilla, Context, and Abstract). During the MI task, subjects were instructed to mentally simulate engaging in activities such as climbing, swimming, and gardening. During the implementation of MT, a 90×60 cm² mirror is positioned between the lower extremities of seated patients. Subsequently, patients engage in active and progressive resistance exercises for the unaffected knee while maintaining the affected knee in a stationary position. As patients progressed, they engaged in active and progressive resistance exercises targeting the affected knee up to their pain threshold. Ultimately, they attained an equal range of motion (ROM) and resistance in both extremities. The TENS therapy was administered under medical supervision using the Intellect device by Chattanooga Group in Hixson, TN, and four distinct self-adhesive electrodes (5.08×5.08 cm, Uni-Patch, Wabasha, MN). The electrodes were placed in a square shape over the area of pain. Conventional TENS was used for 30 minutes at 100 Hz frequency, with a 100 µs pulse width,

and intensity kept below 10% of the motor threshold. The exercise program included warmup, core stability, pelvis and hip stability, gluteus medius strengthening, knee control and stability, knee strengthening exercises, and functional exercises. The home exercise protocol consisted of a 10-minute warm-up with walking, followed by stretches and exercises including straight leg raises, quadriceps setting, pillow squeezes, heel raises, one leg balance, step-ups, and quadriceps strengthening exercises, each performed in three sets of ten repetitions with a 3-minute rest in between sets.

Measures. All measurements were collected at baseline, after treatment, and during the 6-week follow-up for both groups. The only exceptions were sociodemographic characteristics and mental status, which were only assessed before the treatment began.

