Western Ontario and McMaster Universities osteoarthritis index (WOMAC). The assessment of pain, stiffness, and physical function was carried out using the WOMAC, which encompasses 24 items scored on a scale ranging from 0 to 4. Elevated scores are indicative of heightened disability.

Statistical Analysis Plan

Statistical analysis was performed using IBM SPSS version 22.0 software (IBM Corp., Armonk, NY, USA). Qualitative variables were expressed as frequencies and percentages, whereas quantitative variables were presented as means and standard deviations. The normality of the data distribution was evaluated using the Kolmogorov-Smirnov test. Homogeneous

numerical variables were compared using the Independent Samples T-Test, and categorical variables were analyzed using the Chi-Square Test to assess pre-treatment demographic characteristics between groups. Repeated measures ANOVA (rANOVA) was employed to compare baseline (T0), post-treatment (T1), and six-month follow-up (T2) scores, with Bonferroni post hoc analysis conducted to identify the specific sources of differences. A mixed between-within subjects analysis of variance with Tukey's post hoc test was utilized to evaluate the effects of two different treatments (GMI, TENS) across three time points (baseline, post-treatment, and six-month follow-up). In all analyses, statistical significance was set at p<0.05 (two-tailed).

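### Both planned ANOVAs use only patients with all three scores, so a patient with T1 but no T2 is lost from the end-of-treatment comparison

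*Combined protocol and SAP*

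**What the plan says.** The Statistical Analysis Plan describes the within-patient analysis thus: "Repeated measures ANOVA (rANOVA) was employed to compare baseline (T0), post-treatment (T1), and six-month follow-up (T2) scores". Pairwise Bonferroni tests between the time points follow from that model. The between-group analysis is given as "A mixed between-within subjects analysis of variance with Tukey's post hoc test was utilized to evaluate the effects of two different treatments". It covers the same three time points as the within-patient analysis. The software is fixed: "Statistical analysis was performed using IBM SPSS version 22.0 software". The test level is also given: "statistical significance was set at p<0.05 (two-tailed").

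The independent-samples t-test and the chi-square test are limited to pre-treatment characteristics. No comparison at T1 alone is planned. The documents define no analysis population, missing-data method, imputation, dropout allowance or sensitivity analysis.

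Under Design, the protocol calls the trial small and describes the treatment course: "the other group received TENS therapy three times a week for 8 weeks". Under Measures it states: "All measurements were collected at baseline, after treatment, and during the 6-week follow-up for both groups".

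**The concern.** A classical repeated measures or mixed between-within ANOVA works on a full vector of scores per patient. In SPSS the procedure for these models deletes a case that lacks any one of them. The post hoc tests follow from the same models and use the same complete cases. A patient who completes eight weeks of treatment and is measured at T1, but does not return for T2, therefore contributes nothing to the T1 contrast. In the same way, a patient with T2 but no T1 is lost from the T2 contrast.

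Two things are at stake. The first is precision: valid end-of-treatment scores are discarded in a trial that is already small. The second is the comparison itself, which becomes one of completers rather than of the randomised groups. If patients with poor T1 scores skip T2 more often in one arm, the remaining patients flatter that arm.

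**Working it through.** The plan gives no sample size, power, SD or dropout figure, so there is nothing to reproduce. What follows is illustration. From the documents: two arms, three time points, the two ANOVAs, and a two-sided 0.05 level. Assumed: missingness rates, sample size, 1:1 allocation, correlations and missingness mechanism.

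**1. Avoidable loss at T1.** Let each follow-up be missed independently with probability p. The patients lost unnecessarily from the T1 comparison are those with T1 but no T2, a share of (1 - p) × p of those randomised:

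| p | (1 - p) × p |
|---|---|
| 5% | 0.95 × 0.05 = 4.75% |
| 10% | 0.90 × 0.10 = 9% |
| 15% | 0.85 × 0.15 = 12.75% |

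With an assumed 25 per arm and p = 10%, that is 50 × 0.09 = 4.5 patients.

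**2. Precision of the T1 contrast.** Let d be the share of patients with T1 who miss T2. Deleting them multiplies the standard error by 1/√(1 - d). For a contrast that would have 80% power with all T1 scores:

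| d | SE multiplier | Power after deletion |
|---|---|---|
| 5% | 1/√0.95 = 1.026 | 78% |
| 10% | 1/√0.90 = 1.054 | 76% |
| 20% | 1/√0.80 = 1.118 | 71% |

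The power figures do not depend on the sample size, because the effect is set to give 80% at full size.

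**3. Bias and false positives for the planned test.** The simulation assumes 25 per arm, all pairwise correlations 0.5, no true difference, and T2 missingness rising with the T1 score (log-odds 1 per SD) in the GMI arm only. In TENS it is random. Base rates, taken at the mean T1 score, are 10%, 15% and 20%. Higher scores mean worse pain.

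- The bias in the GMI-minus-TENS difference in T0-to-T1 change among completers is about -0.06, -0.08 and -0.10 SD, in favour of GMI.
- The planned group × time test rejects in about 5% to 6.6% of trials, against 5.0% to 5.3% on full data.
- With the same dependence and rate in both arms, or with purely random missingness, the bias is about zero.

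**4. Same dependence, unequal rates.** A separate large simulation assumes VAS SD 2 cm, T1-T2 correlation 0.7, slope 1 per SD in both arms, and 5% missing in one arm. The bias in the T1 mean difference is -0.09 cm when the other arm has 10% missing and -0.25 cm at 20%. Dividing by 2 gives about -0.05 and -0.13 SD. Using every observed T1 score gives about zero in all these scenarios.

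**The case against.** The strongest reply is that nothing in the documents shows that anyone missed T2. The Measures sentence may describe complete collection, although it reads more naturally as a schedule. If nobody missed T2, there is no loss and no bias. That stands, and it makes the harm conditional.

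A second reply is that deletion is not written into the plan: it follows from the named method and software, and imputation beforehand would avoid it. That is true, but no imputation is stated, so the plan as written leads to deletion. It is therefore a consequence of the chosen analysis, and reporting dropouts would not bring the discarded T1 scores back.

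The following stronger readings are tempting but not supported:

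- **That 19% of patients are lost at 10% missing per visit.** The figure 1 - 0.9² = 19% includes the 10% with no T1 score, whom no method can restore to an observed T1 comparison. The avoidable part is 9%.
- **That results are valid only if missing T2 is unrelated to T1.** With no true difference, dependence that is alike in both arms leaves the comparison essentially unbiased.
- **That the false-positive rate reaches 6.7% to 7.5%.** Under the assumptions of step 3, that is the rate for a baseline-adjusted T1 comparison (ANCOVA) in completers, which the plan does not use.
- **That the trial's results are in fact biased.** The documents report no missingness by arm from which to judge this.

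**Conclusion.** The concern holds in a limited form. Under the plan as written, a patient with T1 but no T2 drops out of the end-of-treatment comparison. The loss of precision is modest and follows directly from any such missingness: the T1 standard error rises by about 5% to 12% if 10% to 20% of patients with T1 miss T2. Bias is a possibility rather than a finding. It needs T2 missingness that is related to T1, with a rate or a relation that differs by arm. In the one-arm scenario it is about -0.06 to -0.10 SD, with little inflation of the planned test.

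All these sizes rest on assumed rates, correlations and sample size. Exposure also depends on when T2 takes place. The protocol's Design and Measures sections say six weeks and the Statistical Analysis Plan says six months, and these must be reconciled. A longer interval gives more opportunity for loss.

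The change is worth making because it is cheap and specific, not because harm has been shown.

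**What to change.** Replace the mixed between-within ANOVA with a likelihood-based linear mixed model, fitted with MIXED in the SPSS version already named. The specification should state:

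- **Data:** all available T1 and T2 scores of randomised participants, in their assigned arm, with no exclusion for a missing visit.
- **Terms:** group, time, group × time, and the baseline score as covariate, with the GMI-TENS difference estimated at T1 and at T2.
- **Covariance:** unstructured. With two post-baseline visits this is only two variances and one covariance.
- **Degrees of freedom:** Satterthwaite, because the trial is small.
- **Assumption:** missing at random given the observed scores and arm.
- **Reporting:** the number contributing at each visit, by arm.

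The cost is a change of wording and slightly more modelling work; no new data are needed. The model still relies on missing at random, but this is weaker than what the completers-only analysis assumes. The mixed model itself was not simulated here; the near-zero bias quoted is for comparisons that use all observed T1 scores. As the plan is written in the past tense, the change may have to be made as a reanalysis and labelled as such.

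### Every outcome is tested at 0.05 with no adjustment across outcomes and no primary named, so unless one was registered the chance of a false GMI-TENS difference is about 29-33% at an assumed correlation of 0.5, not 5%

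*Combined protocol and SAP*

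**What the plan says.** The objective, under Objectives, is to find out "whether Graded Motor Imagery (GMI) shows comparable effectiveness to Transcutaneous Electrical Nerve Stimulation (TENS) in improving pain and functionality". It names two broad domains and no variable.

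Under Measures, the repeated assessments cover everything except sociodemographic characteristics and mental status: "All measurements were collected at baseline, after treatment, and during the 6-week follow-up for both groups". They are VAS pain in three conditions, PPT at two points, range of motion (ROM) in two directions, isometric strength of two muscle groups, timed up and go (TUG), and WOMAC covering three domains.

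The Statistical Analysis Plan gives two outcome analyses. The first is a repeated measures ANOVA over the three time points, "with Bonferroni post hoc analysis conducted to identify the specific sources of differences". The second is a mixed ANOVA whose Tukey "post hoc test was utilized to evaluate the effects of two different treatments (GMI, TENS) across three time points". The closing rule is "In all analyses, statistical significance was set at p<0.05 (two-tailed"). The documents do not rank the outcomes, the time points, or the group and group x time effects. They do not say whether WOMAC domains or PPT sites are analysed separately.

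**The concern.** If every outcome is tested at 0.05 and none is designated as decisive, a GMI-TENS difference can be claimed from whichever outcome crosses the line. The error rate for that claim is the chance that at least one outcome crosses, which exceeds 5%.

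The objective makes the rule matter in the other direction too. The question is about comparability, so the same rule allows comparability to be claimed from whichever outcomes fail to cross 0.05. The Design section describes "A small randomized controlled trial design", and in a small trial a non-significant result is weak evidence of anything.

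**Working it through.** The documents state no sample size, power or family-wise error, so there is no figure of theirs to reproduce beyond the per-test 0.05.

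**Step 1: what the named corrections cover.** Bonferroni follows the repeated measures ANOVA and locates differences between time points for one outcome. Tukey follows the mixed ANOVA for one outcome, and with two groups there is only one between-group pair to compare. Neither touches the error that accumulates from one outcome to the next.

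**Step 2: number of outcomes, from Measures.**
- All counted separately: VAS 3 + PPT 2 + ROM 2 + strength 2 + TUG 1 + WOMAC 3 = 13.
- WOMAC as one score: 13 - 2 = 11. PPT sites merged as well: 11 - 1 = 10.
- WOMAC total tested in addition to its domains: 13 + 1 = 14.
- Only the objective's pain and function measures (no ROM or strength): VAS 3 + PPT 1-2 + TUG 1 + WOMAC 1-3 = 6 to 9.

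**Step 3: chance of at least one p<0.05, with no true difference and one between-group test per outcome.**
- Independent outcomes: 1 - 0.95^k. For k = 10, 1 - 0.599 = 0.401. For k = 13, 1 - 0.513 = 0.487.
- Common correlation r: 1 - P(all |Z| < 1.96) for equicorrelated normal test statistics, by numerical integration.

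The documents give no correlations, so each r is an assumption.

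| Outcomes | r = 0 | 0.3 | 0.5 | 0.7 | 0.8 | 0.9 |
|---|---|---|---|---|---|---|
| 6 | 0.265 | 0.241 | 0.207 | 0.164 | 0.139 | 0.108 |
| 9 | 0.370 | 0.326 | 0.269 | 0.202 | 0.166 | 0.124 |
| 10 | 0.401 | 0.351 | 0.287 | 0.213 | 0.173 | 0.128 |
| 11 | 0.431 | 0.375 | 0.304 | 0.223 | 0.180 | 0.131 |
| 13 | 0.487 | 0.418 | 0.334 | 0.241 | 0.192 | 0.138 |
| 14 | 0.512 | 0.438 | 0.348 | 0.249 | 0.197 | 0.141 |

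Simulation agrees for 10 to 13 outcomes. Two-sample t-tests with an assumed 10 to 30 per group gave about 40-49% (independent), 29-35% (r = 0.5) and 13-20% (r = 0.8-0.9). The group x time F test with an assumed 20 per group gave 40-49%, 29-34% and 13-20%.

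**Step 4: do the candidate remedies hold 5%?**
- Holm across all 13 outcomes starts at 0.05/13 = 0.0038. With no true differences, the chance of any false positive is 0.049 if independent and lower with positive correlation.
- A primary at 0.05 followed by Holm on the other 9 or 12 outcomes, with no gate between them, spends 0.05 twice. The chance is about 9.6% if independent, 7.8-7.9% at r = 0.5 and 5.7-5.8% at r = 0.8. A gate is therefore needed.

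**Step 5: what non-significance is worth.** Assume 15 to 40 per group and a true difference of 0.5 SD. A two-sample t-test at 0.05 has power 0.262 to 0.598, so it misses the difference 74% to 40% of the time. At the strictest Holm step for 13 tests, power is 0.053 to 0.238, a miss rate of 95% to 76%. Later Holm steps are less strict.

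**The case against.** The strongest reply is that the trial carries a registry number, and a primary outcome may have been registered there. If so, that outcome's own error is 5%, and the figures above describe only the chance of some false positive among all outcomes. This stands, and the conclusion carries it as a condition.

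A second reply is that the outcomes cannot be independent: three VAS ratings and WOMAC pain come from the same patients. This also stands, and the correlated figures are the ones to use. It does not remove the problem, because the smallest value in the table (6 outcomes, r = 0.9) is 11%, about twice nominal.

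A third reply is that for a comparability objective a false difference is the less relevant error, since it works against the hoped-for conclusion. That is partly right. It is why the fix needs a statement on non-significance alongside the adjustment. However, the SAP declares significance in all analyses, and nothing in it labels the trial exploratory.

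Some stronger readings are tempting but unsupported:
- A reader might infer a rate of 64-74% (1 - 0.95^20 to 1 - 0.95^26) by letting either the group or the group x time effect count. The SAP never says that the group effect may be claimed separately, and the figure also assumes independence.
- A reader might infer from "Date of Document: March 31, 2024", the last day of the stated treatment period, that the analysis was chosen after results were seen. The date does not show that.
- A reader might infer that the three-time-point analysis must give way to a baseline to post-treatment contrast. Controlling the error does not require it.

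**Conclusion.** The concern holds, with a condition. As written, the plan tests 10 to 13 outcomes at two-sided 0.05 with no adjustment across them, and the documents do not say which outcome, time point or effect decides. Unless one primary outcome was prospectively registered, the chance of at least one false GMI-TENS difference is about 29-33% at an assumed correlation of 0.5 and 13-19% at 0.8-0.9. The independent case, 40-49%, is the upper end. If only pain and function measures count, the low end of 6 outcomes gives 21% at 0.5 and 11% at 0.9. All of this assumes no true difference, one between-group test per outcome, and a common correlation that the documents do not supply.

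A reader might go further and say that the trial has no primary outcome at all, or that the SAP ignores multiplicity altogether. Neither is supported. The gap is in these documents and the registry is unseen, and the SAP does adjust within each outcome's ANOVA. This should be corrected, and it can be repaired with data already collected.

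**What to change.** 1. State one deciding between-group test per outcome from the planned mixed ANOVA, for example the group x time effect. State whether WOMAC domains and PPT sites are analysed separately. Together these fix the number of tests.
2. If a primary outcome was prospectively registered, test it at 0.05 at its registered time point. Then either test the others with Holm only if the primary is significant, or report them as exploratory with 95% CIs and no significance claims. If none was registered, apply Holm across all outcomes at a total of 0.05 and report every estimate with a 95% CI. Disclose it if that choice was made after group results were seen.
3. State that a non-significant difference, adjusted or not, is not evidence of comparable effectiveness.

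The cost is SAP wording and a modest re-analysis. Some p-values will no longer count as significant. Holm lowers the power of each test and so makes non-significance more common, which is why item 3 must accompany it.

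One separate matter affects any test that uses the last time point. Design and Measures place follow-up at 6 weeks, while the SAP refers to "baseline (T0), post-treatment (T1), and six-month follow-up (T2) scores". Those passages must be reconciled.
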